#### 5.1.7.1 Complete physical examination

The complete physical examination will include an assessment of the following: general appearance, skin, head and neck (including eyes, ears, nose, mouth, and throat), lymph nodes, abdomen, musculoskeletal (including spine and extremities), cardiovascular, respiratory, and neurological systems.

#### 5.1.7.2 Brief physical examination

The brief physical examination will include an assessment of the general appearance, abdomen, cardiovascular and respiratory system. For the brief physical examination only, information on whether the assessment was performed or not will be recorded.

### 5.1.8 dECG

All ECG assessments must be performed using a digital electrocardiogram (dECG) device. dECGs will be performed in accordance with schedule provided in [Table 1](#). dECG

assessments will be performed prior to blood drawing, spirometry, IP administration and BD administration.

For all subjects, the printouts of the dECG will be collected and signed, dated and stored at the study site along with a signed and dated photocopy of each printout (i.e., if the printout is not on archive-quality paper).

#### **5.1.8.1 Resting 12-lead dECG**

A 12-lead dECG will be taken in supine position, after the subject has been resting for at least 5 minutes. The assessment should be performed before interventions with the subject (e.g., spirometry and administration of asthma-related medications and IP).

A standard dECG with a recommended paper speed of 50 mm/second covering at least 6 sequential beats will be used. The Investigator or authorized delegate will be responsible for the overall interpretation and determination of clinical significance of any potential dECG findings. In case of discrepancy between the Investigator's interpretation and that provided by the dECG machine (if applicable), the Investigator's interpretation takes precedence and should be noted on the printout and recorded in the eCRF. Two identical copies of the dECG will be produced and quality checked and kept in case of further need for re-evaluation.

It is highly recommended that the same machine be used for all dECG assessments throughout the subject's participation in the study.

dECG data and evaluation will be performed by the site Investigator and recorded in the eCRF.

#### **5.1.9 Vital signs**

Pre-dose vital signs (i.e., pulse, blood pressure, respiration rate and body temperature) will be obtained in accordance with schedule provided in [Table 1](#).

Vital signs will be taken prior to blood drawing, IP administration, and, if possible, usual asthma controller medication. At Visits 3 through 6, subjects should be observed for a minimum of 2 hours after IP administration for the appearance of any acute drug reactions. For the remaining visits involving IP administration, subjects will be observed for a minimum of 1 hour after IP administration for any such reaction.

Vital signs should also be taken prior to per protocol BD administration, if applicable for that visit.

##### **5.1.9.1 Pulse, blood pressure and respiration rate**

Pulse rate and blood pressure should be measured after the subject has been resting for at least 5 minutes. The measurement will be taken in sitting position. Pulse rate will be obtained before blood pressure.

Respiration rate will be obtained after subject has been resting for at least 5 minutes, by counting number of breaths (i.e., how many times the chest rises) for one minute.

### **5.1.9.2 Body temperature**

Body temperature will be measured in degrees Celsius prior to IP administration, in accordance with local standards.

## **5.1.10 Other safety assessments**

### **5.1.10.1 Serology**

Hepatitis B surface antigen, hepatitis C antibody, HIV-1 and HIV-2 antibodies will be assessed at enrolment (Visit 1) only. All testing for these will be performed at a central laboratory.

Instructions for sample collection, processing, storage, and shipment will be provided in a separate laboratory manual provided to the sites.

### **5.1.10.2 Infections**

Subjects experiencing a severe infection, defined as/resulting in:

- life-threatening
- requiring hospitalisation
- requiring treatment with antiviral medications, intravenous antibiotics or medications for helminth parasitic infections or,
- a permanent discontinuation of study drug.

All above events must be entered in the infection module in the eCRF.

## **5.2 Other assessments**

### **5.2.1 Weight and height**

Weight and height will be measured in accordance with the schedule provided in [Table 1](#).

The subject's weight will be recorded in kilograms, and height will be recorded in centimetres. Weight and height measurements will be performed in light clothing and with shoes off.

### **5.2.2 Patient reported outcomes**

Patient reported outcomes data will be captured using an ePRO. The device will be paired with a handheld spirometer (peak flow meter) for measuring at-home PEF testing (as outlined

in section 5.1.3). Subjects will be trained on basic ePRO operation will subsequently complete the ACQ-6 during Visit 1. After completing the Visit 1 ACQ-6, the device will remain at the site until Visit 2. At Visit 2, the site staff will set assessment reminder alarms on the device and train the subject on at-home use of the ePRO and handheld spirometer. Training will include explanation of device functionality and proper use of the spirometer. The subject will be asked to use both devices as part of the training and will be asked to verify completion of training on the ePRO device. Subjects will be provided with information on device use and issue resolution (e.g., helpdesk numbers) to conclude the training.

At-home PRO assessment will start the evening of Visit 2. Subjects will be asked to bring the device back to the site for Visits 3 for the baseline assessments at the site. Following Visit 3 all PRO data will be collected at home until Visit 29. Additional details concerning the assessments can be found in the subsequent sections (see sections 5.2.2.1 to 5.2.2.5).

### **5.2.2.1 Asthma Daily Diary**

The Asthma Daily Diary will be completed each day from the evening of Visit 2 to the morning of Visit 29. The Asthma Daily Diary will include the following daily recordings: morning and evening home PEF data (obtained from the home peak flow meter), asthma symptoms, inhalations of rescue medication, nights with awakenings due to asthma symptoms, maintenance medication compliance. There will be triggers in the ePRO device to alert the subjects to signs of worsening of asthma and to contact their physician, please refer to section 5.1.1.

The subject should contact the study physician for evaluation after receiving a diary alert. The investigator/authorized delegate will check subject's adherence to the Asthma Daily Diary at each visit as shown in Table 1.

### **Home PEF measurement**

Details regarding home PEF measurement please refer to section 5.1.3.

### **Asthma symptoms**

Asthma symptoms during night-time and daytime will be recorded by the subject each morning and evening in the Asthma Daily Diary, beginning the evening of Visit 2 until the morning of Visit 29.

Daytime is defined as the time period between the morning lung function assessment (upon rising in the morning) and the evening lung function assessment. Night-time is defined as the time period between the evening lung function assessment (at bedtime) and the morning lung function assessment.

### **Rescue medication**

The number of rescue medication inhalations (puffs) and nebulizer treatments taken will be recorded by the subject in the Asthma Daily Diary twice daily (i.e., in the morning and in the

evening) beginning the evening of Visit 2 until the morning of Visit 29. The number of inhalations taken between the morning and evening lung function assessments will be recorded in the evening. The number of inhalations taken between the evening and the morning will be recorded in the morning.

### **Nocturnal awakenings**

Nocturnal awakenings due to asthma symptoms will be recorded by the subject in the Asthma Daily Diary each morning, beginning in the morning after Visit 2 until the morning of Visit 29, by answering question whether he/she woke up during the night due to asthma symptoms by a “yes” or “no” response.

### **Maintenance medication**

Maintenance medication administration will be recorded in the Asthma Daily Diary once daily in the morning, beginning in the morning after Visit 2 until the morning of Visit 29.

#### **5.2.2.2 Asthma Control Questionnaire (ACQ-6)**

The ACQ-6 is a shortened version of the ACQ that assesses asthma symptoms (night-time waking, symptoms on waking, activity limitation, shortness of breath, wheezing, and short-acting  $\beta_2$ -agonist use) omitting the FEV1 measurement from the original ACQ score.

Subjects will be asked to recall how their asthma has been during the previous week by responding to 1 question regarding their BD use, and 5 questions pertaining to their asthma symptoms.

Questions are weighted equally and scored from 0 (totally controlled) to 6 (severely uncontrolled). The mean ACQ-6 score is the mean of the responses. Mean scores of  $\leq 0.75$  indicate well-controlled asthma, scores between 0.75 and  $\leq 1.5$  indicate partly controlled asthma, and a score  $>1.5$  indicates uncontrolled asthma (Juniper et al 2006). Individual changes of at least 0.5 are considered to be clinically meaningful.

The questionnaire will be completed using the ePRO device.

Visit 1 ACQ-6 scores will determine eligibility for run-in and randomization (see section 3.1 inclusion criterion 11). An initial screening ACQ-6 will be taken at Visit 1 at study site. At Visit 3 subjects will complete ACQ-6. Once randomized, subjects will be asked to complete ACQ-6 once every 2 weeks ( $\pm 1$  day) throughout the treatment period.

The Investigator/authorized delegate will check subject’s adherence to the ACQ-6 at each visit as shown in Table 1.

#### **5.2.2.3 Standardised Asthma Quality of Life Questionnaire for 12 Years and Older (AQLQ(S)+12)**

The AQLQ(S)+12 is a questionnaire that measures the health related quality of health-related quality of life assessment questionnaire developed for asthma subjects ages 12 and above.

The questionnaire comprises 4 separate domains (i.e., asthma symptoms, activity limitations, emotional function, and environmental stimuli).

Subjects will be asked to recall their experiences during the previous 2 weeks and to score each of the questions on a 7-point scale ranging from 7 (no impairment) to 1 (severe impairment). The overall score will be calculated as the mean response to all questions. The 4 individual domain scores (symptoms, activity limitations, emotional function, and environmental stimuli) are the means of the responses to the questions in each of the domains. Individual improvement in both the overall score and individual domain scores of 0.5 has been identified as a minimally important change. The questionnaire will be completed using the subject's ePRO device.

The AQLQ(S)+12 will be first completed by the subject at the site at Visit 3 (Week 0), then every 4 weeks ( $\pm 1$  day) throughout the treatment period. At the EOT visit the AQLQ(S)+12 will be completed during the visit unless completed the day prior.

The Investigator/authorized delegate will check the subject's adherence to AQLQ(S)+12 at each visit as shown in [Table 1](#).

#### **5.2.2.4 Work Productivity and Activity Impairment Questionnaire plus Classroom Impairment Questions (WPAI+CIQ)**

The WPAI+CIQ consists of questions about how asthma and asthma related issues impact a subject's ability to work, attend classes, and perform regular daily activities. The questionnaire relates to the subject's experience over the previous 7 days. The WPAI+CIQ will be used to measure self-reported productivity loss. The questionnaire will be completed using the subject's ePRO device.

The WPAI+CIQ will be first completed at Visit 3 (Week 0), then every 2 weeks ( $\pm 1$  day) at home throughout 52-week treatment period.

The Investigator/authorized delegate will check subject's adherence to WPAI+CIQ at each visit as shown in [Table 1](#).

#### **5.2.2.5 European quality of life-5 dimensions-5 levels (EQ-5D-5L)**

The EQ-5D-5L questionnaire assesses 5 dimensions: mobility, self-care, usual activities, pain/discomfort and anxiety/depression. Each dimension has 5 response options (no problems, slight problems, moderate problems, severe problems, and extreme problems) that reflect increasing levels of difficulty.

The subject will be asked to indicate his/her current health state by selecting the most appropriate level in each of the 5 dimensions. The questionnaire also includes a visual analogue scale, where the subject will be asked to rate current health status on a scale of 0-100, with 0 being the worst imaginable health state

The EQ-5D-5L will be completed weekly (+1 day) starting from Visit 3 (Week 0) throughout Week 52 (Visit 29) using the ePRO device.

The investigator/authorized delegate will check subject's adherence to EQ-5D-5L at each visit as shown in [Table 1](#).

#### **5.2.2.6 Health care resource utilization**

Broad-based health care utilization asthma related event information will be collected by the Investigator/authorized delegate at each visit (as shown in [Table 1](#)) and recorded in the appropriate eCRF module.

At Visit 1, Healthcare Resource Utilization (HRU) information will be collected with a 'one year' recall period. All the subsequent visits will collect HRU information with a recall period of 'since the last scheduled visit'.

**Note:** cases of hospitalization must also be reported as an SAE (as described in sections [6.2](#) and [6.4](#)).

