The final follow up visits (i.e., 30 and 31) are to occur 4 weeks (+7 days) and 20 weeks (+7 days) from the date of the EOT visit, respectively.

Subjects who prematurely discontinue IP (see section 3.9) should return to the study site and complete procedures described for the IP Discontinuation Visit (IPD visit), see Table 1.

At the IP discontinuation visit, the subject will be given three options as to how they will be followed up:

1. Ideally, the subject should return for all regular clinic visits and perform all scheduled assessments until he/she completes a total of 52 weeks in the study, or,
2. The subject will be followed up on a monthly basis via telephone calls while continuing eDiary completion, until the subject completes 52 weeks in the study. No further procedures will be performed. Or,
3. The subject will be contacted at 52 weeks post randomization. No other study assessments will be performed prior to this contact.

For each option, an EOT visit will be conducted.

For option 1, all procedures will be done at each visit as indicated in Table 1. For options 2 and 3, AEs/SAEs, changes in concomitant medications and asthma exacerbation information are the minimum elements that must be collected at each contact.

The subject's decision needs to be documented in the eCRF and the specific section in the ICF/assent form addendum needs to be signed by the subject.

Should the subject choose option 2 or 3 above, they will complete the IP Discontinuation visit immediately and then a follow up telephone call at week 52. If the subject chooses option 1, they will complete the IP Discontinuation visit immediately and then the EOT visit at week 52. The EOT visit/call will be completed immediately in the case of early withdrawal from option 1 or 2.

Subjects who initially chose options 1 or 2 and subsequently cannot or do not wish to comply with the requirements of the chosen option, can choose to continue with a less invasive option (i.e.: Subject initially choosing option 1 can continue with 2 or 3, subjects initially choosing option 2 can continue with 3).

Subjects who do not wish to have any follow up contacts at all, will be discontinued from the study. All discontinued subjects must return the ePRO and ePEF devices at the EOT visit.

Completion, or early termination of IP treatment, will be registered via the IWRS/IVRS for each subject.

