### **8.5 Methods for statistical analyses**

The main focus for the statistical analyses is to compare tralokinumab to placebo in the two pre-defined populations, all subjects and biomarker positive subjects, with regards to primary, key secondary, and safety objectives.

The analysis of the study endpoints will include all data captured during the 52-week double-blind treatment period. This includes data regardless of whether study treatment was prematurely discontinued or delayed, and/or irrespective of protocol adherence, unless the subject withdraws consent or assent to study participation. The statistical analyses will compare tralokinumab to placebo.

Summary data will be presented in tabular format by treatment. Categorical data will be summarized by the number and percentage of subjects in each category. Continuous variables for parametric data will be summarized by descriptive statistics including N, mean, SD, median, and range. All data will be listed. Data listings will be sorted by treatment and subject number.

All hypothesis testing will be reported using 2-sided tests. P-values will be rounded to 4 decimal places.

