#### **8.5.7.7 Health care resource utilization and productivity loss due to asthma**

##### **WPAI-CIQ**

The WPAI+CIQ data will be summarized by treatment, including the 4 types of scores: absenteeism, presenteeism, work/class productivity loss, and activity impairment described. The number and percentage of subjects with asthma specific resource utilization (defined in Section 8.4.3.8) will be presented by treatment group.

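### Health care resource use is not among the data required at the telephone contacts of follow-up options 2 and 3, so the reported percentage of subjects with use may be too low

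*Protocol*

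**What the plan says.** HRU is an other secondary outcome (Protocol Section 2.2), with unscheduled physician visits, unscheduled calls to physicians and use of other asthma medications given as examples. Section 5.2.2.6 fixes when it is collected: "Broad-based health care utilization asthma related event information will be collected by the Investigator/authorized delegate at each visit". After Visit 1, "All the subsequent visits will collect HRU information with a recall period of" the time since the last scheduled visit. Section 8.4.3.7 repeats that collection is at each visit.

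Section 4.2 gives subjects who stop IP early three ways to be followed:

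- Option 1 keeps the visits: "For option 1, all procedures will be done at each visit as indicated in Table 1".
- Option 2 replaces them with calls: "The subject will be followed up on a monthly basis via telephone calls while continuing eDiary completion". It adds that no further procedures take place.
- Option 3 is a single contact: "The subject will be contacted at 52 weeks post randomization. No other study assessments will be performed prior to this contact".

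For options 2 and 3, adverse events together with "changes in concomitant medications and asthma exacerbation information are the minimum elements that must be collected at each contact". HRU is not named.

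The planned summary in Section 8.5.7.7 is "The number and percentage of subjects with asthma specific resource utilization", by treatment group. Section 8.5 describes the analyses as using the data captured in the 52 weeks and adds: "This includes data regardless of whether study treatment was prematurely discontinued or delayed".

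**The concern.** The protocol means to follow subjects for 52 weeks after they stop IP, but for those who move to telephone follow-up it does not require this outcome to be asked about. The summary is a simple percentage of subjects with any use, without adjustment for how long each subject was observed for HRU. If a subject's first unscheduled visit or call comes after the move to telephone, it may never reach the database.

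Two things follow. The percentage in each arm may be too low. If one arm has more telephone follow-up than the other, that arm may look better for a reason unrelated to treatment. A statistical analysis plan can set a denominator, but it cannot recover answers that nobody was required to ask for.

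**Working it through.** **Who is affected.** Only subjects who stop IP and choose option 2 or 3. Option 1 subjects keep all visits, so their HRU collection continues. The protocol does not estimate how many will choose each option. The 15% loss to follow-up in Section 8.2 is a different quantity.

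**What may be lost.** Comparing the HRU content with the required contact content:

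| Type of use | Still captured at option 2/3 contacts? |
|---|---|
| Hospitalization | Yes: also reported as a serious adverse event (5.2.2.6), and these are collected at each contact (4.2) |
| ER or urgent care visit with systemic corticosteroids | Yes: part of the exacerbation information (5.1.1, 4.2) |
| Other asthma medications | Yes: medication changes are collected (4.2) |
| Unscheduled physician visits and calls outside exacerbations | Not required |

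**Week 52.** Section 4.2 states that an end-of-treatment visit takes place under every option, and also that options 2 and 3 end with a telephone call. If there is a visit, HRU would be collected there, and a recall reaching back to the last visit that actually took place would cover the gap. If there is a call, HRU is not required. The text does not settle this.

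**Size.** The protocol states no HRU figure, so there is nothing to reproduce, and what follows is illustration only. Let P be the chance of any use in 52 weeks, Q the chance of any use before the switch, and f the share of an arm on telephone follow-up. Assume that no HRU is recorded after the switch and that everyone stays in the denominator. Then

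- shortfall in one arm = f × (P − Q);
- difference between arms with no treatment effect = (f₂ − f₁) × (P − Q).

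Model A: Poisson contacts at rate λ per year, with the switch at mid-year. P = 1 − exp(−λ), Q = 1 − exp(−λ/2). Shares 10% and 20%.

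| λ | P | Q | 0.10 × (P − Q) |
|---|---|---|---|
| 0.5 | 39.3% | 22.1% | 1.7 points |
| 0.8 | 55.1% | 33.0% | 2.2 points |
| 1.5 | 77.7% | 52.8% | 2.5 points |

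At λ = 0.8 the table would show 0.9 × 55.1 + 0.1 × 33.0 = 52.9% against 0.8 × 55.1 + 0.2 × 33.0 = 50.6%.

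Model B: constant hazard of first use, with the switch uniform over the year. L = −ln(1 − P), Q = 1 − (1 − exp(−L))/L. Shares 5% and 15%.

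| P | Q | P − Q | 0.10 × (P − Q) |
|---|---|---|---|
| 20% | 10.4% | 9.6 | 1.0 points |
| 40% | 21.7% | 18.3 | 1.8 points |
| 60% | 34.5% | 25.5 | 2.5 points |

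Under Model B the shortfall within one arm, for f from 5% to 15%, is 0.5 to 1.4 points at P = 20%, 0.9 to 2.7 at 40% and 1.3 to 3.8 at 60%.

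Both models overstate the loss, because part of HRU is captured by other routes. If a fraction c of the subjects whose first use falls after the switch is still picked up, every figure is multiplied by (1 − c); at an assumed c of one half, 2.2 points becomes 1.1. With equal shares in the two arms and no treatment effect, the between-arm difference is zero.

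**The case against.** The strongest reply is that the loss is narrow and the plan does not forbid closing it. The contact list is a minimum, so a site may ask about HRU by telephone. Option 1, described as the ideal, is unaffected. Hospital stays, exacerbation-related emergency visits and medication changes are recorded under every option. One statement in Section 4.2 promises an end-of-treatment visit in all cases. Keeping the lighter options short is a defensible way to prevent complete withdrawal, which Section 3.9.1 wants to avoid. All of this stands and limits the point. It does not remove it: collection left to each site will vary, and the wording of option 2 discourages it.

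A reader might go further in three ways that the document does not support.

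- **That these subjects count as non-users after stopping.** Section 8.5.7.7 states no denominator and no rule for absent HRU records, matters that may be in the analysis plan. A subject with use recorded before the switch remains a user in any case.
- **That Section 8.5 is contradicted.** It speaks of data captured, and so does not promise data that were never collected.
- **That the recall period loses an interval whenever a visit is missed.** This needs the last scheduled visit to mean one that did not take place. The more natural meaning is the last scheduled, as opposed to unscheduled, visit that occurred.

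**Conclusion.** The point holds in a limited form. HRU is not required at option 2 and 3 contacts, so unscheduled physician visits and calls outside exacerbations may be under-recorded after the switch. The percentage of subjects with use may then be biased low, and the comparison biased if telephone follow-up differs by arm.

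The range of about 1 to 2.5 points is not an estimate for this trial. It rests on assumed event rates or use proportions, an assumed 10-point imbalance between arms, complete loss after the switch and retention of all subjects in the denominator. The rate of 0.8 in the middle row of Model A happens to equal the placebo exacerbation rate assumed in Section 8.2, yet exacerbations are exactly what the calls do capture.

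The outcome is summarised descriptively and lies outside the testing hierarchy of Section 8.5.1, so no confirmatory conclusion depends on it. This is a minor improvement.

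**What to change.** In Section 4.2, add HRU to the minimum elements collected at each option 2 and option 3 contact, including Week 52, and set the recall for these contacts to the time since HRU was last collected. In the same section, reconcile the statement that every option has an end-of-treatment visit with the statement that options 2 and 3 end in a telephone call.

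For contacts already made, state with the summary in Section 8.5.7.7 which subjects form the denominator and how long they were observed for HRU. The reference there to Section 8.4.3.8, which covers the productivity questionnaire, can be changed in the same edit to Section 8.4.3.7, which covers HRU.

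The cost is a few questions at calls that already take place and an eCRF page opened for telephone contacts. The small drawback is longer recall for option 3 subjects, who are asked only once, at Week 52.
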